4.5.2.2. Vital Signs

A summary of change from baseline vital sign values will be provided by visit and treatment group, including systolic blood pressure, diastolic blood pressure, heart rate and temperature.

Summaries of vital sign results relative to PCI criteria will also be provided. The summary will include baseline, planned visit and worst-case post baseline.

4.5.2.3. ECG

The baseline ECG will be taken as the mean of the triplicate values collected pre-dose on Day 1. The following will be summarised by visit: ECG findings and change from baseline in ECG values.

The number of subjects with maximum QTc values at baseline and post-baseline relative to baseline will be summarized using the following categories: No Change or Decrease To ≤ 450 , Any Increase > 450 , Increase To > 450 to ≤ 480 , Increase To > 480 to ≤ 500 , and Increase To > 500 .

The changes in QTc values will be categorized into the clinical concern ranges which are specific to changes in QTc: Increase of ≤ 30 , 31-60 and > 60 msec. A summary of change in QTc value will display the number and percentage of subjects with a change within each range for the worst-case post-baseline only. Subjects with missing baseline values will be excluded from this summary.

4.6. Other Analyses

4.6.1. Subgroup analyses

No formal subgroup analyses are planned.

4.7. Interim Analyses

The GSK Biostatistics Team (including Third Party Suppliers) and GSK CPMS Team (including Third Party Suppliers) will be unblinded to all subjects already randomised at the time of the interim analyses and will process and analyse the data.

Results (group summaries and if required, individual summaries) may be shared internally within GSK as deemed necessary to inform the clinical development plan and prepare supporting documents for the potential phase 2 study. Data from the interim analyses may also be shared externally with regulators (e.g., via an interim CSR) as required to support the potential phase 2 study.

Until the time of the primary PK and TE analysis (all participants completed Day 57), access to the results for interim analyses conducted at an earlier timepoint (excluding CPMS and Biostatistics) will be documented in a separate document which will detail the individuals or groups within GSK who reviewed the data (i.e. name and function, type of data, purpose and date). This document will be stored in the TMF.

No changes to the conduct of the study will be implemented as a result of the interim analyses.

4.7.1. Day 57 Analysis

Alongside the primary PK and TE analysis, an interim analysis of safety data will occur once all participants have completed Day 57. The planned interim analyses will be performed as detailed in Section 4.5 with the full list of outputs being produced specified in the OPS.

This data will be assessed in an unblinded manner and used to support regulatory submissions. No changes to the conduct of the study will be implemented as a result of the interim analyses.

As the primary purpose of the interim analyses is to provide safety data alongside primary PK data to regulators – to support China and Japan’s potential participation in GSK3858279’s phase 2 programs – data at both an individual and aggregate treatment group level will be provided.

4.7.2. Other

Prior to the primary PK and TE analysis, an additional interim analysis including Study Population, Safety, TE and PK data may be performed to support regulatory submissions. The data will be assessed in an unblinded manner. No changes to the conduct of the study will be implemented as a result of the interim analyses.

This interim analysis will occur on all available data at a specified timepoint. This timepoint will be decided by the central study team in conjunction with the Chinese and Japanese LOCs.

As the primary purpose of the interim analyses is to provide Safety and PK data to regulators – to support China and Japan’s potential participation in GSK3858279’s phase 2 programs – data at both an individual and aggregate treatment group level will be provided.

The full list of outputs being produced by the GSK Biostatistics Team (including Third Party Suppliers) for inclusion in this interim analysis are detailed in the OPS. GSK CPMS Team (including Third Party Suppliers) will produce additional outputs as appropriate.

4.8. Changes to Protocol Defined Analyses

The protocol specified that interim analysis details, including what data will be reviewed, the level of unblinding and who will have access to the data, would be documented in an interim charter. This information has been included in Section 4.7 and a separate interim analysis charter will not be produced.

Changes from the originally planned statistical analysis specified in the protocol are detailed in [Table 2](#)

Table 2 Changes to Protocol Defined Analysis Plan

Protocol Defined Analysis	SAP Defined Analysis	Rationale for Changes
Section 9.2.3: “Primary analysis will be performed on the PK parameters AUC (0-56) post-dose and Cmax. The parameters will be \log_e transformed and then analysed using a mixed model, with ethnicity and body weight included as covariates. Geometric mean and 90% confidence intervals will be calculated for each of the ethnic cohorts, along with the comparisons for Japanese/Caucasians and Chinese/Caucasians.”	Section 4.2.1.2: “The PK parameters will be \log_e transformed and analysed using a mixed model. Terms fitted in the model will include ethnicity and $\log_e(\text{body weight})$. An additional model including the ethnicity term only will be fitted.”	
 • Inclusion of additional analysis without body weight to be presented alongside the original model • Inclusion of $\log_e(\text{bodyweight})$ instead of bodyweight as linear relationship expected between PK parameters and \log_e (bodyweight)

5. SAMPLE SIZE DETERMINATION

Approximately 10 participants are to be randomized (7 active: 3 placebo) per cohort to ensure that a minimum of 6 participants on active and 2 on placebo per cohort are evaluable. An evaluable participant is one that has been dosed and has safety and all PK data up to Day 57. Replacements (assigned to the same treatment) are permitted at the discretion of the sponsor in consultation with the investigator.

[figure not shown]
CCI

CCI

CONFIDENTIAL

212979

CCI

6. SUPPORTING DOCUMENTATION

6.1. Appendix 1 Study Population Analyses

Unless otherwise specified, the study population analyses will be based on the Screened, Enrolled or Randomised Analysis Sets. A summary of the number of participants in each of the participant level analysis set will be provided.

6.1.1. Participant Disposition

A summary of the number and percentage of participants who completed the study as well as those who prematurely withdrew from the study will be provided. Reasons for study withdrawal will be summarized. For those who have neither completed nor withdrawn, they will be categorized as ongoing. A participant is considered to have completed the study if they have completed all planned study assessments including the follow-up visit.

Rescreening of screen failures is allowed as per protocol. Rescreened participants will be summarized under their latest participant number.

6.1.2. Demographic and Baseline Characteristics

The demographic characteristics including age, gender, ethnicity, height/weight at screening, Body Mass Index (BMI) and race will be summarized with descriptive statistics. In addition, the following age categories will be summarized: 18-64, 65-84 and ≥ 85 based on the Enrolled Analysis Set.

6.1.3. Protocol Deviations

Important protocol deviations will be summarized and include overall important protocol deviations, COVID-19 related important protocol deviations and non COVID-19 related important protocol deviations.

Protocol deviations will be tracked by the study team throughout the conduct of the study. These protocol deviations will be reviewed to identify those considered as important as follows:

- Data will be reviewed prior to unblinding and freezing the database to ensure all important deviations (where possible without knowing the study intervention details) are captured and categorised in the protocol deviations dataset.
- This dataset will be the basis for the summaries of important protocol deviations.

Visits and assessments missed due to the COVID-19 pandemic, together with visits conducted remotely, will be summarized in both a table and a figure.

6.1.4. Prior and Concomitant Medications

Concomitant medications will be coded using both the GSK Drug and WHO Drug dictionaries. However, the summary will be based on GSK Drug dictionary only. The summary of concomitant medications will be provided by ingredient, i.e. multi-ingredient medications will be summarized for each individual ingredient rather than a combination of ingredients. The summary will be created using ingredient base names, i.e. ingredients with the same base name but different salt will appear under one base name in the summary.

Prior medication is any medication or vaccine (including over-the-counter or prescription medicines, recreational drugs, vitamins, and/or herbal supplements) or other specific categories of interest without missing end date and with end date >7 days prior to dosing.

Concomitant medication is any medication or vaccine (including over-the-counter or prescription medicines, recreational drugs, vitamins, and/or herbal supplements) or other specific categories of interest, that is not considered prior.

6.1.5. Additional Analyses Due to the COVID-19 Pandemic

A participant is defined as having a suspected, probable or confirmed COVID-19 infection during the study if the answer is “Confirmed”, “Probable” or “Suspected” to the case diagnosis question from the COVID-19 coronavirus infection assessment eCRF. Numbers of participants with a suspected, probable or confirmed COVID-19 infection, and of COVID-19 test results will be summarized.

6.2. Appendix 2 Data Derivations Rule

6.2.1. Criteria for Potential Clinical Importance

6.2.1.1. Vital Signs

Vital Sign Parameter (Absolute)	Units	Clinical Concern Range	
		Lower	Upper
Systolic Blood Pressure	mmHg	< 85	> 160
Diastolic Blood Pressure	mmHg	< 45	> 100
Heart Rate	bpm	< 40	> 110
Body Temperature	°C	≤ 35.5	> 38.0

6.2.1.2. Laboratory Values

Haematology				
Laboratory Parameter	Units	Category	Clinical Concern Range	
			Low Flag (< x)	High Flag (>x)
Hematocrit	Ratio of 1	Male	0.39	0.54
		Female	0.35	0.49
		Δ from BL	↓ 0.075	
Hemoglobin	g/L	Male	124	180
		Female	109	180
		Δ from BL	↓ 25	
Lymphocytes	x10 ⁹ / L		0.75	
Neutrophil Count	x10 ⁹ / L		1.5	
Platelet Count	x10 ⁹ / L		100	550
White Blood Cell Count (WBC)	x10 ⁹ / L		2.5	20

Clinical Chemistry				
Laboratory Parameter	Units	Category	Clinical Concern Range	
			Low Flag (< x)	High Flag (>x)
Albumin	g/L		30	
Calcium	mmol/L		2	2.75
Creatinine	umol/L			1.3 X ULN
Creatinine	umol/L	Δ from BL		↑ 44.2
Glucose	mmol/L		3	9
Potassium	mmol/L		3	5.5
Sodium	mmol/L		130	150
Total CO ₂	mmol/L		18	32
Creatinine Kinase	mg/dL			>1.6 X ULN
C-reactive Protein	mg/L			≥ 3.0
Troponin T	ng/ml			14.1
NT-pro BNP	ng/L			125.99

Urinalysis	
A subject is considered to have urinalysis results of PCI, if they have abnormal microscopic examination.	

Liver Function			
Test Analyte	Units	Category	Clinical Concern Range
ALT/SGPT	IU/L	High	$\geq 2 \times \text{ULN}$
AST/SGOT	IU/L	High	$\geq 2 \times \text{ULN}$
AlkPhos	IU/L	High	$\geq 2 \times \text{ULN}$
T Bilirubin	$\mu\text{mol/L}$	High	$\geq 1.5 \times \text{ULN}$
T. Bilirubin + ALT	$\mu\text{mol/L}$ IU/L	High	ALT $\geq 3 \times \text{ULN}$ AND bilirubin $\geq 1.5 \times \text{ULN}$

6.2.1.3. ECG

ECG Parameter	Units	Clinical Concern Range	
		Lower	Upper
Absolute			
Absolute QTc Interval	msec		> 500
Absolute PR Interval	msec	< 110	> 220
Absolute QRS Interval	msec	< 75	> 120
Change from Baseline			
Increase from Baseline QTc	msec		> 60

6.2.2. Study Phase

Assessments and events will be classified according to the time of occurrence relative to the study intervention period.

Pre-Intervention is defined as time prior to the single dose of study intervention.

On-Intervention is defined as time following single dose. If time of assessment (e.g. ECG, Lab, vital signs) is not collected and assessment date is the same as the dose date, the assessment is considered pre-intervention. If time of study intervention (e.g. AE, concomitant medication) is not collected and the start/end date is the same as dose date, it is considered on-intervention.

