AE= adverse event; ECG= Electrocardiogram, SC = subcutaneous; PD = pharmacodynamics, PK= pharmacokinetics; SAE= serious adverse event, TE = Target engagement

* Visits optional for Chinese and Japanese participants

^a ± 2hrs

^b ± 1 day

^c ± 4 day

- 1 Early withdrawal
- 2 Re-check clinical status before dose of study medication
- 3 Prior to dosing
- 4 pre-dose and 60 mins post start of SC injections
- 5 pre-dose, 30 mins, 1h, 2h, 3h & 4 h post start of SC injections
- 6 NT-pro BNP. NB: Troponin I at all time points
- 7 Result to be available prior to dose of study drug. Day -2 for PCR or rapid antigen test
- 8 Study intervention administered as 4 separate injections
- 9 Only TE sample
- 10 PK and TE blood samples taken pre-dose, 6h, 12h, 24h, 36h and 48h post start of SC injections, respectively
- 11 Blood sample to be taken pre-dose
- 12 Taken pre-dose

- The timing of planned study assessments may change during the course of the study based on emerging data/in-stream data review (e.g., to obtain data closer to the time of peak plasma concentrations) to ensure appropriate monitoring.
- Any changes in the timing of time points for any planned study assessments as the result of emerging pharmacokinetic/pharmacodynamic data from this study must be documented and approved by the relevant study team member and then archived in the sponsor and site study files but will not constitute a protocol amendment.
- The Competent Authority (CA) and ethics committee (EC) will be informed of any safety issues that constitute a substantial amendment and require alteration of the safety monitoring scheme or amendment of the informed consent form (ICF). The changes will be approved by the CA and the EC before implementation.

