4.1.2. Baseline Definition

For all endpoints the baseline value will be the latest pre-dose assessment with a non-missing value, including those from unscheduled visits. If time is not collected, Day 1 assessments are assumed to be taken prior to first dose and used as baseline.

The CCL17 levels (free, total) baseline value will be derived by averaging the two pre-dose measurements (Day -2 and Day 1 pre-dose).

Unless otherwise stated, if baseline data is missing no derivation will be performed and baseline will be set to missing.

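### Day 1 vital signs and ECGs without a recorded time default to pre-dose, even when their planned time point is after the dose

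*SAP*

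**What the plan says.** Two SAP sections deal with a Day 1 measurement that has no clock time.

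- SAP 6.2.2 (Study Phase): "If time of assessment (e.g. ECG, Lab, vital signs) is not collected and assessment date is the same as the dose date", it is assigned to the pre-intervention phase.
- SAP 4.1.2 (Baseline Definition): "If time is not collected, Day 1 assessments are assumed to be taken prior to first dose and used as baseline". The general definition in the same section is that "the baseline value will be the latest pre-dose assessment with a non-missing value", and unscheduled visits are included.

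The protocol's Schedule of Activities (1.3) repeats two of the named assessments on Day 1. Footnote 5 sets vital signs at "pre-dose, 30 mins, 1h, 2h, 3h & 4 h post start of SC injections". Footnote 4 sets triplicate ECGs at "pre-dose and 60 mins post start of SC injections". The Day 1 haematology, chemistry and urinalysis entry carries no timing footnote.

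Two other SAP provisions limit the effect. Section 4.5.2.3 gives ECG its own baseline: "The baseline ECG will be taken as the mean of the triplicate values collected pre-dose on Day 1". Section 6.2.4 lays out by-visit tables by the name of the scheduled visit, with the worst post-baseline value shown alongside.

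**The concern.** Assuming pre-dose is sensible for a test done once on Day 1 before the injections. It does not suit vital signs, where most Day 1 sets are planned after the dose. A record labelled as the 4-hour set already shows that it is post-dose, but the two fallback sentences look only at the clock time.

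Clinically important changes in vital signs and ECG are among the primary safety endpoints (SAP 4.2), and the hours after the injections are when an acute reaction would be expected to show. The default also runs against the SAP's handling of other missing safety information. The next sentence of 6.2.2 places untimed adverse events and medications on the dose date in the on-intervention phase, and 4.5.1 counts an event with missing relatedness as related. For vital signs and ECG, missing information instead moves a measurement out of the post-dose period.

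**Working it through.** The plan gives no figure to reproduce here, so the check applies the two SAP rules literally to the Day 1 schedule.

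**Inputs.** Day 1 vital signs (SoA footnote 5): 1 pre-dose set and 5 post-dose sets. Day 1 ECG (SoA footnote 4): 1 pre-dose and 1 post-dose triplicate. Planned size (SAP 5): about 10 per cohort, 7 active and 3 placebo, in 3 cohorts, so 3 × 10 = 30 in all and 3 × 7 = 21 on active.

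**Share of Day 1 sets that are post-dose.** Vital signs 5/6 = 83%; ECG 1/2 = 50%.

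**Phase assigned under SAP 6.2.2.**

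| Assessment | All times recorded: pre / on | No times recorded: pre / on |
|---|---|---|
| Vital signs | 1 / 5 | 6 / 0 |
| ECG | 1 / 1 | 2 / 0 |

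**Baseline under SAP 4.1.2.** With no times recorded, all six vital-sign sets are eligible, and the last in planned order is the 4-hour set. If only one post-dose set is untimed, it is assumed pre-dose and eligible as baseline. The SAP does not say how to order it against the timed pre-dose set, so it could become baseline, but the text does not settle this. For ECG, section 4.5.2.3 keeps baseline at the pre-dose triplicate.

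**Worst-case summaries.** A record classed as pre-intervention is no longer a candidate for the worst post-baseline value. Taking a value out of a maximum or minimum can only make it less extreme or leave it as it was. One untimed vital-sign set leaves 5 − 1 = 4 Day 1 post-dose sets in play; an untimed 60-minute ECG leaves 1 − 1 = 0 on Day 1. Later visits still contribute in both cases.

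**Later changes from a wrong vital-sign baseline.** If the misplaced value differs from the true baseline by d, every later change for that participant is off by −d. One such participant moves the mean of a 7-participant group by −d/7. The documents give no value for d. Assuming d = +10 mmHg gives −1.4 mmHg, and d = −10 gives +1.4; d = +20 gives −2.9, and d = −20 gives +2.9. The sign follows the sign of d.

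**Upper bound on records exposed, if every time were missing.** Vital signs 30 × 5 = 150 sets (21 × 5 = 105 on active); ECG 30 × 1 = 30 sets (21 on active). This is a ceiling, not an expectation.

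**The case against.** The strongest reply is that the rule may never operate. It applies only when the time is not collected, which could mean forms with no time field. Sets planned at 30 minutes, 1, 2, 3 and 4 hours have to be worked by the clock. The protocol says that actual times are recorded for the dose and for PK and target-engagement samples (8.4, 8.5) and is silent for vital signs (8.2.2) and ECG (8.2.3). Silence does not show that times are missing, and CRF completion guidance sits in a manual outside these documents (10.1.8). This stands, and it is why the impact is rated low. It does not remove the gap in the written rule.

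The consequences are also limited. The vital-sign limits for potential clinical importance are absolute (SAP 6.2.1.1), so a wrong baseline does not change later flags. A clinically significant vital-sign or ECG abnormality is an adverse event (Protocol 10.3.1), and an event starting on the dose date counts as emergent (SAP 4.5.1), so an acute reaction would still be reported there. Both points stand.

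A reader might infer more than the documents support:

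- **That ECG baselines are contaminated.** SAP 4.5.2.3 ties them to the pre-dose triplicate.
- **That laboratory results are affected.** No post-dose laboratory time point is scheduled on Day 1.
- **That the record disappears from every table.** By-visit tables follow the scheduled visit name and may still show it.
- **That the error always hides effects.** This is true of the worst-case summaries only; the effect of a wrong baseline on later changes can go either way.

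**Conclusion.** The gap is real but narrow, and its impact is low. As written, SAP 4.1.2 and 6.2.2 would misclassify an untimed post-dose vital-sign set or 60-minute ECG on Day 1. For vital signs, the record could become baseline and would drop out of the worst-case summary. For ECG, it would drop out of the worst-case QTc summaries only.

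The conclusion rests on a literal reading of the two sections and on at least one such time being missing. The documents give no rate for that, and it may be zero. The shifts in the group mean shown above rest on assumed values and are not estimates for this trial. No hypothesis is tested and the safety reporting is descriptive, so no formal inference depends on this point.

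**What to change.** In SAP 4.1.2 and 6.2.2, state that when clock time is missing on Day 1 the record is classified by its planned time point:

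- Only records labelled pre-dose are eligible as baseline. The 30-minute to 4-hour vital signs and the 60-minute ECG are on-intervention.
- The assume-pre-dose rule is kept only for scheduled assessments collected once on Day 1 with no planned post-dose time point.
- Untimed unscheduled Day 1 records are not used as baseline. They have no planned time point to fall back on, and 4.1.2 now admits them.

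The cost is a few sentences of SAP text, with no new data collection, provided the planned time point is held on each record. It is best done before the next unblinded analysis.

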6.2.3. Study Day and Reference Dates

The safety reference date is the study intervention start date and will be used to calculate study day for safety measures.

The study day is calculated as below:

Assessment Date = Missing \rightarrow Study Day = Missing

Assessment Date $<$ Reference Date \rightarrow Study Day = Assessment Date – Ref Date

Assessment Date \geq Reference Date \rightarrow Study Day = Assessment Date – Ref Date + 1

6.2.4. Assessment Window

For data summaries by visit, scheduled visits with nominal visit description as well as the worst-case post baseline will be displayed. Unscheduled visits will not be displayed or slotted into a visit window but will be included in the derivation of worst-case post baseline assessment. All unscheduled visits will be displayed in the listing.

6.2.5. Multiple measurements at One Analysis Time Point

When triplicate ECG assessments are taken, mean of the measurement will be calculated first and summary statistics will be based on the calculated mean. This will apply to both baseline and post baseline assessments.

6.2.6. Handling of Partial Dates

Element	Reporting Detail					
General	
 Partial dates will be displayed as captured in participant listing displays. However, where necessary, display macros may impute dates as temporary variables for sorting data in listings only. In addition, partial dates may be imputed for 'slotting' data to study phases or for specific analysis purposes as outlined below. Imputed partial dates will not be used to derive study day, time to onset or duration (e.g., time to onset or duration of adverse events), or elapsed time variables (e.g., time since diagnosis). 					
Adverse Events	
 Partial dates for AE recorded in the CRF will be imputed using the following conventions: 
 
 Missing start day	 
If study intervention start date is missing (i.e. participant did not start study intervention), then set start date = 1st of month.
 
Else if study intervention start date is not missing:
 
 If month and year of start date = month and year of study intervention start date, then 
 If stop date contains a full date and stop date is earlier than study intervention start date, then set start date= 1st of month. Else set start date = study intervention start date. 
Else set start date = 1st of month.
 	
 
 Missing start day and month	If study intervention start date is missing (i.e. participant did not start study intervention), then set start date =	
 
		Missing start day	
If study intervention start date is missing (i.e. participant did not start study intervention), then set start date = 1st of month.
 
Else if study intervention start date is not missing:
 
 If month and year of start date = month and year of study intervention start date, then 
 If stop date contains a full date and stop date is earlier than study intervention start date, then set start date= 1st of month. Else set start date = study intervention start date. 
Else set start date = 1st of month.
	Missing start day and month	If study intervention start date is missing (i.e. participant did not start study intervention), then set start date =
Missing start day	
If study intervention start date is missing (i.e. participant did not start study intervention), then set start date = 1st of month.
 
Else if study intervention start date is not missing:
 
 If month and year of start date = month and year of study intervention start date, then 
 If stop date contains a full date and stop date is earlier than study intervention start date, then set start date= 1st of month. Else set start date = study intervention start date. 
Else set start date = 1st of month.
					
Missing start day and month	If study intervention start date is missing (i.e. participant did not start study intervention), then set start date =					

Element	Reporting Detail					
		
January 1.
 
Else if study intervention start date is not missing:
 
 ○ If year of start date = year of study intervention start date, then 
 ▪ If stop date contains a full date and stop date is earlier than study intervention start date, then set start date = January 1. ▪ Else set start date = study intervention start date. 
Else set start date = January 1.
				
	Missing end day	A '28/29/30/31' will be used for the day (dependent on the month and year).				
	Missing end day and month	No Imputation				
	Completely missing start/end date	No imputation				
Concomitant Medications/ Medical History		
 ● Partial dates for any concomitant medications recorded in the CRF will be imputed using the following convention: 
 
 Missing start day	 
If study intervention start date is missing (i.e. participant did not start study intervention), then set start date = 1st of month.
 
Else if study intervention start date is not missing:
 
 ○ If month and year of start date = month and year of study intervention start date, then 
 ▪ If stop date contains a full date and stop date is earlier than study intervention start date, then set start date= 1st of month. ▪ Else set start date = study intervention start date. 
Else set start date = 1st of month.
 	
 
 Missing start	If study intervention start date is missing (i.e.	
 
	Missing start day	
If study intervention start date is missing (i.e. participant did not start study intervention), then set start date = 1st of month.
 
Else if study intervention start date is not missing:
 
 ○ If month and year of start date = month and year of study intervention start date, then 
 ▪ If stop date contains a full date and stop date is earlier than study intervention start date, then set start date= 1st of month. ▪ Else set start date = study intervention start date. 
Else set start date = 1st of month.
	Missing start	If study intervention start date is missing (i.e.
Missing start day	
If study intervention start date is missing (i.e. participant did not start study intervention), then set start date = 1st of month.
 
Else if study intervention start date is not missing:
 
 ○ If month and year of start date = month and year of study intervention start date, then 
 ▪ If stop date contains a full date and stop date is earlier than study intervention start date, then set start date= 1st of month. ▪ Else set start date = study intervention start date. 
Else set start date = 1st of month.
					
Missing start	If study intervention start date is missing (i.e.					

Element	Reporting Detail
	
day and month
 
participant did not start study intervention), then set start date = January 1.
 
Else if study intervention start date is not missing:
 
 ○ If year of start date = year of study intervention start date, then 
 ▪ If stop date contains a full date and stop date is earlier than study intervention start date, then set start date = January 1. ▪ Else set start date = study. intervention start date. 
Else set start date = January 1.

	Missing end day
	A '28/29/30/31' will be used for the day (dependent on the month and year).
	Missing end day and month
	A '31' will be used for the day and 'Dec' will be used for the month.
	Completely missing start/end date
	No imputation

Trademarks

Trademarks of the GlaxoSmithKline Group of Companies	Trademarks not owned by the GlaxoSmithKline Group of Companies
None	
NONMEM
 
WinNonlin

